Detection of any association between pre-transplant comorbidity and post-transplant HRQoL, can improve the selection process of older transplant candidates by including the comorbidity score as part of the patient selection algorithm.

Aim 3:

To investigate the relationship between pre-transplant comorbidity, expressed as the Liu comorbidity index, pre-transplant HRQoL described by KDQOL-SF and post-transplant patient- and graft survival.

Aim 4:

To evaluate kidney transplantation in older patients in a health economic perspective, including evaluation of quality adjusted life years (QALY), and investigate if QALY values are changing over time. By collecting standard cost estimates for the different procedures, we should be able to calculate an incremental cost-effectiveness ratio (ICER) for kidney transplantation versus dialysis

This aim will provide further information about the benefits kidney transplantation can or cannot provide older patients from a health economic perspective. This analysis will be of major importance for present and future priority discussions.

4. Implementation

Data will be retrieved from the QUESTION65 database described previously, and the Norwegian Renal Registry. Missing data will be retrieved from the patient records at Oslo University Hospital, Rikshospitalet and from the patients' local hospital records. The key necessary for identification of patients will be stored at the registry and will not be available for the researchers.

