4.1. Design, methods and analyses

Statistics

All statistical analyses will be performed using the statistical software package SPSS Statistics version 22 or later. Scores from KDQOL-SF will be calculated and compared using traditional statistical methods (two-sided unpaired t-test or paired t-test, ANOVA, logistic regression). Fisher's exact test will be used to analyze binary data. Other standard statistical methods as for example multiple variable logistic regression analyses will be used as needed. Survival analyses will be performed using the Kaplan-Meier method and Cox proportional hazard models.

Aim 1:

Data collection: Patient reported outcomes are collected in an on-going, prospective, longitudinal study (QUESTION65). By the end of inclusions in December 2016, we estimate that 280 patients should be included. All patients give their written informed consent before inclusion in the study. In addition, all patients have signed an informed consent when they were included in the Norwegian Renal Registry. This allows the use of unidentified data from the registry in research protocols.

HRQoL is assessed using the KDQOL-SF-36 health Survey (20, 21). This survey consists of two parts, a generic (SF-36) and disease specific (KDQOL) part. The same questionnaire is used before and after transplantation. The results will also be compared with data from an age matched Norwegian cohort (22).

All patients over the age of 65 years, who are accepted for the kidney transplantation waiting list or living donor transplantation, receive an invitation to participate in the study. In addition to provide baseline data, all patients receive additional forms with the same questionnaires every sixth months until they are transplanted, permanently removed from the transplant waiting list or deceased. Patients who are transplanted will receive a discharge form from Rikshospitalet (10 weeks after transplantation), after six months and at one-, three-, five-, seven- and ten years post-transplant.

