Statistical power: The primary objective of the study is to detect differences in the QOL dimension general health (GH). According to the literature, SF-36 scores for GH varies between 47 and 69 for transplanted patients and between 36 and 44 for patients treated in haemodialysis (10, 23, 24). The standard deviation in these studies varies between 15 and 25. A clinically significant difference in SF-36 GH score is estimated to be around 10%. With a predicted SF-36 GH score of 50 for transplanted patients and 40 for patients in haemodialysis, we need a minimum of 63 patients to complete the study to reach a significance level (α) of 5% and a power (β) of 80%. According to previous analyses, 80% of patients > 70 years who are accepted for the kidney transplantation wait list will eventually be transplanted and five year survival in this age group is 64% (5). Consequently, a minimum of 100 patients must be transplanted and hence, an even higher number must be included at baseline. To have the possibility to evaluate the impact of gender and dialysis modality, the number of included patients has been further increased up to a total of 280. The regional committee of medical and health research ethics have approved this increase.

By August 2016, 261 patients are included, 152 are transplanted. Consequently, the number included and transplanted patients are already well above the minimum number.

Aim 2:

Data collection: From 2012 we have included pre-transplant data according to the Liu comorbidity index (17) as part of the routine work up of candidates for kidney transplantation. Complete data describing patient and transplant characteristics, including the Liu comorbidity index will be

Date of Update: April 5. 2020

extracted from the Norwegian Renal Registry. The data will be exported from the registry without any identification except from a patient number. Post-transplant HRQoL values will be retrieved from the QUESTION65 database.

Statistical power: No previous studies describing the correlation between pre-transplant comorbidity and post-transplant HRQoL exist. Based on the same considerations as described for Aim 1, a similar number of patients should be necessary for Aim 2 to reach a significance level of 5% and a power of 80%.

Aim 3:

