Data collection: Complete data describing patient and transplant characteristics, including the Liu comorbidity index will be extracted from the Norwegian Renal Registry as described for Aim 2. Pre-transplant HRQoL will be retrieved from the QUESTION65 database. Post-transplant survival data will be extracted from the Norwegian Renal Registry. The data will be exported from the registry without any identification except from a patient number.

Statistical power: No previous studies describing the correlation between pre-transplant comorbidity, pre-transplant HRQoL and post-transplant survival exist. Based on previous analyses on similar patient cohorts (25), 150 patients should be sufficient to detect statistically significant associations.

Aim 4:

Data collection: QALYs will be calculated from the SF-36 (SF-6D) scores available in the QUESTION65 database. From the SF-6D, a health index can be calculated. Patients who die during follow-up will have health index = 0 from time of death, and with this health index, QALYs can be calculated for each patient during follow-up. Costs necessary for estimation of cost/QALY and ICER will be estimated through use of information from the patient records at the patients' local hospitals as well as Oslo University Hospital. DRG weighted costs will be used for each contact (in-patient, out-patient and dialysis). In addition, medication costs will be estimated based on each patient's medication list and travel costs will be estimated based on the distance between the patient's home and the hospital.

Statistical power: No previous studies evaluating QALY in older kidney transplant recipients exist. Power calculation is therefore difficult to perform.

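### The itemised costing rule for Aim 4 contains no donor cost, so as written the ICER of transplantation versus dialysis omits a cost that every transplant incurs

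*Combined protocol and SAP*

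**What the plan says.** Section 3, Aim 4, sets out to "calculate an incremental cost-effectiveness ratio (ICER) for kidney transplantation versus dialysis". It describes the route in general terms: "By collecting standard cost estimates for the different procedures, we should be able to calculate an incremental cost-effectiveness ratio (ICER". No procedures are listed there.

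The itemised rule is in section 4.1, Aim 4, under data collection. Costs "will be estimated through use of information from the patient records at the patients' local hospitals as well as Oslo University Hospital". The unit cost is then defined: "DRG weighted costs will be used for each contact (in-patient, out-patient and dialysis". Two further items complete the list: "medication costs will be estimated based on each patient's medication list and travel costs will be estimated based on the distance" from home to hospital.

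Two statements elsewhere in section 4.1 bear on this. Under Aim 1, data collection, patients over 65 who are "accepted for the kidney transplantation waiting list or living donor transplantation, receive an invitation to participate in the study". Under Aim 1, statistical power, the sample was enlarged "To have the possibility to evaluate the impact of gender and dialysis modality".

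**The concern.** Every element of the itemised rule attaches to the study patient: that patient's contacts, medication list and travel. The donor is a different person, and the donor's care would not appear as a contact in the recipient's record. No part of the plan that could be read mentions donor work-up, nephrectomy, organ retrieval or donor follow-up, and no costing perspective is stated that would justify leaving them out.

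The gap is not confined to living donors, because a deceased-donor kidney also has to be procured. The cost falls on the transplant side only, so leaving it out favours transplantation in the ICER.

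The result is intended to inform prioritisation (section 3, Aim 4), at a time when section 2.1 reports that an upper age limit for recipients is a possibility. An ICER that omits a one-sided cost is open to challenge in that debate, whatever the omission's size.

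**Working it through.** The plan states no cost, QALY gain or ICER for Aim 4, so there is no figure to reproduce. The check compares the listed items with what each side incurs, and then works out the direction and form of the error.

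**Step 1. Items in the rule (section 4.1, Aim 4) against costs incurred**

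- Recipient's in-patient and out-patient contacts: listed, both sides.
- Dialysis contacts: listed as a category of their own; setting not stated.
- Medication and travel: listed, both sides.
- Living-donor work-up, nephrectomy and follow-up: not listed.
- Deceased-donor procurement: not listed.
- Standard costs for procedures (section 3, Aim 4): mentioned, but no donor item is named.
- Donor share inside the transplant DRG weight: not stated.

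**Step 2. Effect on the ICER**

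Let C and Q be mean cost and mean QALYs, with T for transplantation and D for dialysis:

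ICER = (C_T − C_D) / (Q_T − Q_D)

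If a donor cost d per transplant is missing from C_T, then

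true ICER − planned ICER = d / (Q_T − Q_D).

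This is positive whenever transplantation gains QALYs, so the planned ICER is too low.

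**Step 3. Illustration on assumed values**

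Neither d nor the QALY gain is in the documents. I assume d = NOK 100,000 to 300,000 and a gain of 1 to 2 QALYs:

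- 100,000 / 2 = NOK 50,000 per QALY
- 100,000 / 1 = NOK 100,000 per QALY
- 300,000 / 2 = NOK 150,000 per QALY
- 300,000 / 1 = NOK 300,000 per QALY
- d = 0 (donor cost already in the DRG weight): no shift

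**Step 4. Secondary point: dialysis without a hospital contact**

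If some dialysis time produced no contact and was not costed by another route, let h be the uncounted cost per patient on the dialysis side, net of any on the transplant side. The shift becomes (d − h) / (Q_T − Q_D). Take one year of hospital dialysis as the unit of cost, and assume home dialysis costs 0.8 a year and is wholly uncounted, so that h = home share × 0.8 × years:

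- d = 0.5, share 10%, 3 years: 0.5 − 0.24 = +0.26
- d = 0.5, share 20%, 3 years: 0.5 − 0.48 = +0.02
- d = 0.5, share 30%, 5 years: 0.5 − 1.20 = −0.70

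With d from 0 to 1.0, share from 0 to 30% and 3 to 5 years, d − h runs from −1.20 to +1.00. The two possible omissions pull in opposite directions, and the documents cannot fix the net sign.

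**The case against.** The strongest reply is that the itemised rule need not be exhaustive. The general statement under Aim 4 in section 3 is open-ended and could cover donor procedures. The DRG weight for the transplant stay might also include donor cost, in which case a separate item would count it twice. In addition, the text between the Aim 4 power statement and section 4.3 was not available to me and could hold further costing detail. These points stand as limits: they make the bias conditional. They do not remove the gap. The one place where cost components are itemised has no donor item, and nothing that I could read says that the DRG weight covers it.

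A reader might go further and infer that home dialysis is left out, that cost per QALY is therefore biased on both sides, and that a comparison by modality would show home dialysis as almost free. The documents do not support this:

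- Dialysis is a named cost category with no restriction to hospital treatment. No text that I could read mentions home dialysis or its share, and the medication list may capture some of the supplies.
- Even if both items were missing, the errors would oppose each other in the incremental cost, as step 4 shows.
- The remark about dialysis modality explains the sample size under Aim 1. Aim 4 plans no cost comparison by modality.

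What remains of that reading is that the method for such dialysis time is not stated.

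**Conclusion.** The point holds for donor costs. Followed as written, the Aim 4 rule omits them, and the transplant cost and the ICER are understated by donor cost divided by incremental QALYs. This rests on two conditions: that the transplant DRG weight does not already carry the cost, and that transplantation gains QALYs. The documents give nothing to size the error, and the NOK range in step 3 rests wholly on assumed inputs. Because a costing rule is present and the missing item falls on one side only, this is more than a request for detail.

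For dialysis without a hospital contact, the supported conclusion is narrower: the costing method is unspecified. Neither an omission nor a direction of bias is shown.

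**What to change.** 1. Find out whether the DRG weight for the transplant stay includes any donor cost, and state the answer in the Aim 4 rule.
2. Add one standard donor unit cost per transplant, by donor type, to the transplant side. For living donors it covers work-up, nephrectomy and follow-up; for deceased donors, procurement. Include only the part that the DRG weight does not already cover.
3. Report the ICER with and without the donor item as a sensitivity analysis.
4. State how dialysis that generates no hospital contact is costed. For any such time, use a cost per day on that modality, excluding supplies already on the medication list. This needs modality dates from the Norwegian Renal Registry or the patient records. The plan does not confirm that the registry holds them, so this should be checked first.

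The cost is small: a few tariff figures, no review of donor records, and a link to modality dates if they exist. Section 4.4 schedules Aim 4 data collection through 2022, after the April 2020 update, which leaves time for the change. The downside is that cost per QALY for transplantation becomes less favourable on the donor item.

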4.3. Budget

Budget (in NOK 1000)	2019	2020*	2021	2022	Total
Personnel costs (PhD student)	955	0	955	955	2865
Travel grant	30	0	30	30	90
Other operating costs: Courses, Literature	15	0	15	15	45
Total	1000	0	1000	1000	3000

* No expences registered for 2020 because the PhD student is on maternity leave

4.4. Schedule:

Activity	2019	2020	2021	2022
Data collection of HRQoL study - aim 1	x			
Data collection - aim 2	x	x	x	
Data collection - aim 3	x	x	x	
Data collection - aim 4	x	x	x	x
Data analysis	x	x	x	x
Publication		x	x	x
Writing PhD thesis				x
Dissertation for the degree of PhD				x

Date of Update: April 5. 2020

Five years HRQoL data will be available for the first patient in 2018 and by the end of 2020, the database is expected to be complete also with long-term data necessary for evaluating long-term HRQoL (aim 1). Data from the other aims will be available for analysis and evaluation from 2019.

Planned publications: All manuscripts will be published in international nephrology, transplant or geriatric journals. Abstracts will be presented at international meetings.

Tentative papers:

1. Changes in health-related quality of life in older kidney transplant recipient up to three years post-transplant (2020)
2. Association between pre-transplant comorbidity and health related quality of life in older kidney transplant recipients (2021)
3. Association between pre-transplant comorbidity, pre-transplant health related quality of life and long-term (three years) post-transplant survival in kidney transplant recipients older than 65 years (2021)
4. Cost-effectiveness of kidney transplantation in the elderly (2022)

4.5 Implementation plan:

Results from our study will have implications for clinicians in selection and treatment of elderly patients with chronic kidney disease throughout the world. With increasing transplantation wait lists and organ scarcity it is important to give organs to the “most suitable candidates”. The aging of the general population means that older people now account for much greater proportion of patients with or at risk for kidney disease and kidney failure. Chronological age alone is not sufficient as the basis for clinical decision and a more nuanced approach is required – based on comorbidities, quality of life and obviously preference of each patient. Improved selection of the elderly population with ESRD will obviously also profit the younger recipients waiting for a kidney transplant. New knowledge about this group of patients can provide better information both to the patients and their health providers.

5. Patient involvement:

The first PhD protocol from this project;” Does kidney transplantation in older patients add life to years (Question 65)” was supported by the Norwegian patient organization for patients with kidney disease and transplant recipients (Landsforeningen for nyresyke og transplanterte, LNT) through a PhD grant from the Extra foundation. LNT is also involved in the new protocol and the results will be presented for the patient organization at meetings and in their magazine “LNT nytt.”

In addition, the project has been presented and discussed in the Telemark Hospital Research Committee, the members of which include a patients' representative.

6. Ethical considerations:

No experimental treatment is planned. As a consequence, it is considered to be ethical correct to include more patients than are required as a minimum. A higher number of patients included will provide more robust results. Informed consent will be obtained from all included patients. Each patient will receive a unique identification number that will be used for identification of individual data. The key necessary to identify the patients will be stored at Rikshospitalet (Section of

Date of Update: April 5. 2020

Nephrology) and will not be available for the involved researchers. The sub-protocol for the longitudinal evaluation of HRQoL (Aim 1) has been approved by the regional committee for medical and health research ethics (2012/527). Data collection for Aim 1 started in 2012 and was completed in November 2016.

